### 9.2 Randomisation method

Randomisation will be done by SPSS, statistics 20 with an allocation ratio of 1:1 between groups. Once a number is assigned to a patient, the investigator will open the treatment regimen assignment and the subject will receive treatment according to the assigned strategy. The numbers are anonymous dispensed in closed envelopes and stored at department of pulmonary diseases Medical Center Alkmaar. The main-investigator will be responsible for maintaining the storage and allocation of the envelopes.

### **9.3 Analysis populations**

#### **9.3.1 Clinical Intent-To-Treat analysis (ITT)**

All randomized patients with non CF-bronchiectasis will be included in the final ITT-population.

#### **9.3.2 Modified Intent-To-Treat analysis (mITT)**

The patients who are randomised but dropped out from the study directly after the tolerance test due to a moderate-severe bronchial obstruction or a severe cough, are excluded from the mITT analysis. So the mITT population includes the patients who passed the tolerance test with TIS or placebo according to the randomisation.

#### **9.3.3 Per protocol Treatment analysis (PTT)**

All randomized patients who received and completed treatment according to study protocol will be included in the per protocol analysis. Patients will be considered as non-evaluable if they do not complete a total treatment for at least 9 months. Termination of the study or incomplete data collection is also defined as non-evaluable.

### **9.4 Methods of analysis**

#### **9.4.1 General statistical considerations**

All data will be collected and analysed using SPSS statistics 20.

Statistical analysis will be performed on an intent-to-treat basis by the investigator and an independent statistician. All continuous variables will be tested for normal distribution with the Kolmogorov-Smirnov test for normal distribution. The Student-t test will be used for normally distributed variables, the Mann-Whitney U test for not normally distributed variables and the  $\chi^2$  test for dichotomous variables. The software package SPSS 20 for Windows (IBM-SPSS Inc., Chicago, Illinois, USA) is available for statistical analysis. A value of  $p < 0.05$  will be considered significant.

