#### **7.1.3 Other study parameters (if applicable)**

Other objectives of the study are age of the patients, sex, tobacco and alcohol use, number of patients with COPD or other etiologies, and the biomarkers like C-reactive protein level and leukocytes in serum, liver function and renal function. In addition to these objectives, it is also interesting how much patients withdrew from the study because of bronchospasm or other adverse effects, supplementary use of oral antibiotics due to an exacerbation, azithromycin maintenance and pseudomonas carriage. An exacerbation will be noticed by using the diary card weekly. If there are any changes in medical

condition and compliance with medication, this will be noticed by using the diary card. In subjects who experience a pulmonary exacerbation, the own GP or respiratory physician will assess the severity of pulmonary symptoms and signs and prescribes antibiotics and/or medication (e.g. prednisolone, bronchodilators). If so, the investigator will be informed. At least also an objective of the study is hospitalization and duration of the hospitalization.

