#### **9.4.3 Primary study parameter(s)**

A poisson regression model was used to analyse the primary outcome measure, evaluating both events and exposure (person-time), employing a quasilikelihood factor (with overdispersion correction), and incorporating the following covariables: treatment assignment, age, sex, smoking history, and presence of *P aeruginosa* and azithromycin maintenance use at baseline.

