#### **9.4.5 Other study parameters**

Baseline comparison of the treatment groups with regard to demographic variables (such as age, gender, number of co-morbidities, smoking, alcohol use, etc.) and time of TIS treatment. These parameters will be assessed by using the Student-t test for normally distributed variables, and the Mann-Whitney U test for not normally distributed variables.

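### Hospitalisation and supplementary antibiotics have no stated method, so the default tests in 9.4.1 apply; these ignore follow-up time and are biased if follow-up is lost unequally between arms

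*Combined protocol and SAP*

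**What the plan says.** Section 7.1.3 lists, among the other study parameters, "supplementary use of oral antibiotics due to an exacerbation", and adds: "At least also an objective of the study is hospitalization and duration of the hospitalization". The methods are then divided as follows.

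- **9.4.1 (general rule, intent-to-treat basis):** "The Student-t test will be used for normally distributed variables, the Mann-Whitney U test for not normally distributed variables", and the chi-square "test for dichotomous variables".
- **9.4.3 (primary endpoint):** a Poisson model "evaluating both events and exposure (person-time), employing a quasilikelihood factor (with overdispersion correction", with treatment and five baseline covariates.
- **9.4.4 (secondary endpoints):** Cox regression for time to first exacerbation; linear mixed models for lung function and quality of life.
- **9.4.5 (other study parameters):** "These parameters will be assessed by using the Student-t test for normally distributed variables", otherwise Mann-Whitney. The parameters meant are those in the sentence before, namely demographic variables and time on TIS. Hospitalisation and antibiotic use are not among them.

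On follow-up, 4.4 and 9.1 assume 30% drop-out and then say that it was higher than expected. Patients may leave the study at any time (7.4). Patients with moderate to severe obstruction at the visit 1 tolerance test, which is done after randomisation with the assigned product, are excluded from the study (7.3). They remain in the ITT set (9.3.1) and are removed from the mITT set (9.3.2). Sections 7.3 and 7.6 ask that patients who stop treatment be followed on the full schedule; sections 3 and 5.3 encourage this but accept an early termination visit as the minimum.

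**The concern.** Admissions, hospital days and antibiotic courses accumulate with time under observation. A t test or Mann-Whitney test on the raw numbers, or a chi-square test on any versus none, treats a patient seen for a few weeks without an event the same as one seen for 52 weeks without an event. The plan recognises this for exacerbations by modelling person-time, but it carries the idea no further.

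The gap is sharpest for antibiotic courses. Under 7.3 an exacerbation counts only if the physician agrees that antibiotic and/or prednisolone therapy is needed, so antibiotic courses for an exacerbation are largely the same events as the primary endpoint. They would be adjusted for exposure in one table and not in the next. If one arm loses more follow-up, the raw comparison shows fewer events in that arm without any treatment effect.

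**Working it through.** The plan gives no figure for these parameters, so there is none to reproduce. The check asks how far the default tests go wrong when there is no treatment effect.

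**Inputs from the documents.** 29 patients per arm (section 3); drop-out 30% or more (4.4); 52 weeks of treatment; exacerbation rate 2.1 per year with SD 1.6 (9.1), which gives an overdispersion of 1.6²/2.1 = 1.22.

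**Assumptions.** The documents give no drop-out by arm, no timing of drop-out and no admission rate. Loss of follow-up is taken as 40% v 20% (30% overall), with 50% v 10% as a more extreme case and 30% v 30% as the reference. Every leaver is taken as lost from then on, with the events counted up to that time.

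**Step 1: bias in the raw count.** Let d be the share lost and f the mean fraction of the year that leavers complete. Mean follow-up per patient is m = 1 − d + d·f. With a common event rate in both arms, the expected count is rate × m, so the ratio of mean counts is m(A)/m(B). The person-time rate ratio stays at 1.

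| Loss A v B | f | m(A) | m(B) | Count ratio |
|---|---|---|---|---|
| 40% v 20% | 0.10 | 1 − 0.40 + 0.04 = 0.64 | 1 − 0.20 + 0.02 = 0.82 | 0.78 |
| 40% v 20% | 0.25 | 0.70 | 0.85 | 0.82 |
| 40% v 20% | 0.50 | 0.80 | 0.90 | 0.89 |
| 50% v 10% | 0.125 | 0.5625 | 0.9125 | 0.62 |
| 50% v 10% | 0.50 | 0.75 | 0.95 | 0.79 |
| 30% v 30% | any | equal | equal | 1.00 |

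At 40% v 20% the arm with more loss shows a false reduction of 11% to 22%. The event rate does not enter the ratio, so the same holds for rare admissions and for hospital days.

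**Step 2: false-positive rate.** Overdispersed counts were simulated under no effect, 29 per arm, two-sided 5% level (4,000 runs; 2,000 for the offset model, which had treatment only). Leavers go either evenly over the year or all within 13 weeks (f = 0.125).

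| Events per year | Loss and timing | t | Mann-Whitney | Chi-square | Quasi-Poisson with offset |
|---|---|---|---|---|---|
| 2.1 | 30% v 30%, even | 5.0% | 5.0% | 5.3% | 5.4% |
| 2.1 | 40% v 20%, even | 8.0% | 8.2% | 7.1% | 5.8% |
| 2.1 | 40% v 20%, 13 weeks | 14.5% | 16.4% | 15.9% | 5.6% |
| 0.5 | 40% v 20%, even | 6.2% | 6.2% | 5.9% | 5.0% |
| 0.5 | 40% v 20%, 13 weeks | 7.7% | 8.1% | 7.9% | 6.0% |
| 0.2 | 40% v 20%, even | 5.1% | 5.6% | 5.9% | 2.3% |
| 0.2 | 40% v 20%, 13 weeks | 6.3% | 7.1% | 7.5% | 2.4% |

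The rate of 2.1 is a stand-in for antibiotic courses, because they overlap with exacerbations. The rates 0.5 and 0.2 are assumed for admissions. For admissions the tests are only mildly inflated at 40% v 20%; the distortion lies mainly in the estimate.

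**Step 3: how many covariates admissions can carry.** Person-time at 40% v 20% is 29 × (0.64 + 0.82) = 42.3 to 29 × (0.80 + 0.90) = 49.3 years. At 0.2 to 0.5 admissions per year that is 42.3 × 0.2 = 8.5 up to 49.3 × 0.5 = 24.7 admissions. This is too few for the six terms of the 9.4.3 model.

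**The case against.** The strongest reply is that this is a small specification gap, not a wrong analysis. Several parts of that reply stand.

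- **Assignment is by default.** A reader might infer from 9.4.5 that the plan prescribes t and Mann-Whitney tests for admissions and antibiotics. It does not: its sentence refers to demographics and time on TIS. Section 9.4.1 is generic and does not mention event counts. But no other stated rule reaches these parameters, and if another method was intended, it still has to be written down.
- **The direction is not established.** A reader might infer that the TIS arm will lose more follow-up, so that the bias favours TIS. In the table in 6.3 only wheeze has a placebo comparison (50% v 15%). Bronchospasm (10%) and dyspnoea (32%) are given for tobramycin alone, and the nine withdrawals come from an open-label study. The studies of tobramycin solution for inhalation used twice-daily dosing, unlike this trial. The reason given for the extra drop-out (4.4) is the treatment and cleaning burden, which both arms share. Exclusion on the assigned product after randomisation makes unequal loss plausible, no more.
- **Stopping treatment is not leaving the study.** Follow-up under 7.3 and 7.6 would recover much of the lost time, and the mITT set removes the tolerance-test failures. Neither helps with patients who leave later, and 9.4.1 names ITT as the basis.
- **Stakes are limited.** These are other parameters without a stated hypothesis, and 7.1.3 speaks of antibiotic use without saying that courses are counted.

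**Conclusion.** The concern holds in a conditional form. The plan names no method for hospitalisation or supplementary antibiotics, and the only rule that reaches them ignores follow-up time in a trial with drop-out of 30% or more. If loss is unequal, the raw comparison is biased: a count ratio of about 0.78 to 0.89 under no effect at an assumed 40% v 20%. This is an upper bound for that split and timing, since it treats every leaver as fully lost. With equal loss there is no bias. The documents do not show which case applies, so they do not support saying that these results will favour TIS. The primary endpoint is unaffected. The change is worth making because the plan already contains the methods needed.

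**What to change.** Add a paragraph to 9.4.5:

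- Analyse the number of admissions and the number of antibiotic courses by quasi-Poisson regression with log person-time as offset, as in 9.4.3. For admissions use treatment only, or minimal covariates, because events will be few.
- Analyse any hospitalisation as time to first admission with the Cox model used in 9.4.4.
- Report admissions, antibiotic courses and hospital days per patient-year by arm, together with follow-up time and drop-out by arm.
- State that the t, Mann-Whitney and chi-square rule is for variables that do not accumulate with time.

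The cost is one paragraph and a little more analysis work. It needs the date on which each patient's follow-up ends, which the person-time in 9.4.3 already requires. There are two limits. An offset corrects for unequal follow-up but not for informative drop-out, where patients who leave have a different event rate from those who stay; the table of drop-out by arm lets readers judge that. With very few admissions the quasi-Poisson test is conservative (about 2% at 0.2 per year in the simulation), so the rates and intervals should carry the message rather than the p-value.

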#### **4.4 Sample size calculation**

The hypothesis is that prolonged treatment with tobramycin reduces the number of exacerbations per patient by 50%. This reduction seems clinically relevant and is based on the assumption that maintenance treatment with TIS OD as well as intermittent TIS BID is comparable to that of azithromycin treatment. This assumption is derived from the data of the BAT trial (placebo: mean 2,1 exacerbations (sd 1.6); azithromycin: mean 0,8 exacerbations (sd 1.1). The reduction in percentage is used for the determination of trial size.

We used a poisson regression model to determine group size. For type I error and type II error 0.05 and 0.2 were used respectively. The hypothesis will be tested two sided. With a baseline exacerbation rate of 2.1 in the placebo group and an expected response rate ratio of 0.5 with an exposure time of 1 year a total of 18 evaluable patients are required to be on each treatment arm.

With a drop-out percentage of 30% we must include totally 48 (24 patients per group) patients.

Due to unforeseen reasons we initially include two extra patients per group. But after the interim analysis three extra patients will be included in the study, because the drop-off percentage is higher as expected in advance. Reason for discontinuation of the study is the intensive treatment and cleaning schedule of the inhaled study medication. So, with a total of 58 patients (29 per group) with bronchiectasis, and not the initially 52 patients (26 per group), we expect to achieve the intended effect size.

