#### **7.1.2 Secondary study parameters/endpoints (if applicable)**

The secondary objective of this study is to evaluate the effect of TIS treatment on time to next exacerbation, airflow limitation (FVC% predicted, FEV1% predicted), LRTI-VAS, Quality of Life-Bronchiectasis (QOL-B), Leicester cough score, bacterial load in sputum and tobramycin resistance, including MIC values, depending on the capabilities of the microbiological laboratory.

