#### **Run-in (Visit 0, week -4)**

At the baseline visit (- 4 weeks), subjects will be deemed eligible for the study after the clinical diagnosis bronchiectasis has been made, and the study has been explained to them. The following procedures will be completed:

- Verify inclusion/exclusion criteria
- Obtain written informed consent (alternatively at visit 1)
- Record medical history
- Collection of demographic information, concurrent disease, concomitant medication use, and previous course(s) of antibiotic therapy in the preceding year
- Physical examination (including sputum characteristics, cough, dyspnoea, pleuritic chest pain, chills or rigors, and lung sounds) and vital signs (respiratory rate, heart rate, blood pressure, body temperature and oxygen saturation)
- Laboratory examination (CRP, Hb, WBC, Sodium, Potassium, Creatinin, eGFR, Liver Function Tests, extra blood sample(s) will be taken and frozen for future research)
- Sputum culture (semi-quantitative)
- Randomisation (or at visit 1)

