#### **Day 1 (Visit 1)**

- Record medical history
- Assessment of LRTI-VAS
- Quality of Life-Bronchiectasis (QOL-B) questionnaire
- Leicester cough score
- Physical examination (including sputum characteristics, cough, dyspnoea, pleuritic chest pain, chills or rigors, and lung sounds) and vital signs (respiratory rate, heart rate, blood pressure, body temperature and oxygen saturation)

- Collection of demographic information, concurrent disease, concomitant medication use, and previous course(s) of antibiotic therapy in the preceding year
- Spirometry according to the standard criteria of the European Respiratory Society
- Concomitant medication monitoring
- Study drug and Innospire deluxe dispensation
- Inhalation tolerance test with either TIS or placebo (depending on randomisation) and first dose of study drug administered under supervision of study staff
- Instructions on proper administration and return of study drug and proper care of the nebulizer
- Diary card instruction

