#### **9.4.4 Secondary study parameter(s)**

Time to first exacerbation during the treatment period, as well as during the wash-out period, will be assessed using Cox proportional hazards regression and reported graphically using Kaplan-Meier estimates.

Statistical significance in change of FEV1 (percent of predicted) and FVC (percent of predicted) attributable to treatment will be calculated with a linear mixed-model analysis. The effect of time on outcome variables will be checked for linearity by means of plots and model Proportional hazards assumptions will be tested with log-minus-log plots. Time will be entered as an interval variable, with the number of intervals depending on the frequency of follow-up visits at which the outcome will be measured. Predefined confounders are entered stepwise as fixed effects. Predictors remain in the regression equation if the model fit increases significantly. Thereafter, random effects will be explored for intercept (patients) and slope (time and patients). If random effects do not change the model fit significantly, a fixed effect will be assumed. Change in quality of life was analyzed using linear mixed-model analysis as well. The minimal important difference (MID) in bronchiectasis was reported only for the Quality Of Life-Bronchiectasis questionnaire (QOL-B), with a minimal important difference (MID) for the Respiratory symptoms scale of 8 points represent clinical relevance. The MID for the leicester cough questionnaire in chronic cough is 1.3 points in total and represent clinical relevance. The Leicester cough questionnaire was initially developed for patients with chronic cough, but has been validated in patients with bronchiectasis. Consequently, the minimal important difference of 1.3 points will be used in this study and represent clinical relevance. Secondary to these questionnaires the LRTI-VAS questionnaire will be used. This questionnaire is a validated and reliable tool for symptom measurement in non-CF bronchiectasis.

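### Sputum bacterial load, a listed secondary endpoint, has no named analysis and falls to a general two-sample rule that specifies no use of the baseline culture

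*Combined protocol and SAP*

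**What the plan says.** Section 7.1.2 lists among the secondary endpoints LRTI-VAS, QOL-B, the Leicester cough score, and "bacterial load in sputum and tobramycin resistance, including MIC values". The Summary names bacterial load among the outcomes expected to show a significant benefit.

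Section 9.4.4 gives Cox regression for time to first exacerbation, and a linear mixed model for FEV1, FVC and quality of life. It does not mention bacterial load. LRTI-VAS appears at the end of the quality-of-life text: "Secondary to these questionnaires the LRTI-VAS questionnaire will be used".

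The general rule is in 9.4.1. Continuous variables are first put through a Kolmogorov-Smirnov test, and then: "The Student-t test will be used for normally distributed variables, the Mann-Whitney U test for not normally distributed variables". The rule has no baseline term and no time point. It does not say whether the test is run on the follow-up value or on the change.

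Baseline values exist for both endpoints. The run-in visit lists "Sputum culture (semi-quantitative" (the bracket closes there), and Day 1 lists "Assessment of LRTI-VAS". Follow-up sputum is taken at weeks 26, 52 and 56. Section 3 describes the microbiological measure as a semi-quantitative density.

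**The concern.** For bacterial load, the general rule in 9.4.1 is either the planned analysis by default or no analysis is planned at all. Three things are unsatisfactory if it is the default.

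- **Baseline.** A two-sample test on the follow-up grade leaves chance imbalance in the baseline grade inside the comparison. With at most 29 patients per arm that imbalance can be material, and the measurement that would remove it is already collected.
- **Scale.** A semi-quantitative culture result is an ordered grade, so testing it for normality tells the analyst nothing useful.
- **Pre-specification.** A rule that lets the data pick the test, and leaves open follow-up or change and which visit, does not fix the analysis in advance.

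At stake is power, and freedom from post hoc choice, for one secondary endpoint. The primary analysis in 9.4.3 has its own covariate-adjusted model and is not affected.

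**Working it through.** **1. The plan's own figure.** The only calculated sample size is for the exacerbation rate (4.4 and 9.1), at two-sided alpha 0.05 and 80% power. Its rate inputs read: "With a baseline exacerbation rate of 2.1 in the placebo group and an expected response rate ratio of 0.5". Allocation is equal, each patient contributes 1 year and over-dispersion is set to 1, so the Poisson regression formula is

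N = (1.960·√V0 + 0.842·√V1)² / (T · rate · ln(RR)²), where V0 = 4 and V1 = 2 + 2/0.5 = 6.

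N = (3.920 + 2.062)² / (1 × 2.1 × 0.4805) = 35.78 / 1.009 = 35.46, rounded up to 36. This agrees with the plan. The 80% power therefore belongs to exacerbations. No effect size, SD, correlation or power is given for bacterial load or LRTI-VAS.

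**2. Which rule applies.**

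| Secondary endpoint | Method named in 9.4.4 |
|---|---|
| Time to exacerbation | Cox regression |
| FEV1, FVC | Linear mixed model |
| Quality of life | Linear mixed model |
| LRTI-VAS | Placed in the quality-of-life text, no model of its own |
| Bacterial load | None |

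Section 9.4.5 repeats the t or Mann-Whitney rule for demographic variables, so 9.4.1 is not confined to descriptive data.

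**3. What baseline adjustment would gain for bacterial load.** Assumptions, none of them in the documents except the arm size: 29 per arm; a normal latent load at baseline and follow-up with correlation r, cut into five grades; treatment shift 0.65 SD; two-sided 0.05; 3000 simulated trials per setting.

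| r | Mann-Whitney, follow-up | Mann-Whitney, change | Rank analysis of covariance | Gain over follow-up |
|---|---|---|---|---|
| 0.3 | 62% | 44% | 65% | 3 |
| 0.4 | 64% | 51% | 69% | 5 |
| 0.5 | 62% | 54% | 70% | 8 |
| 0.6 | 63% | 63% | 76% | 13 |
| 0.7 | 62% | 74% | 85% | 23 |

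The Monte Carlo error of one power figure near 62% is √(0.62 × 0.38 / 3000) ≈ 0.9 points. Repeat runs put the gain at r = 0.7 between 20 and 23, so the range is stated as about 3 to 22 points. With 20 per arm (29 × 0.7 ≈ 20, the plan's 30% drop-out) the gains run from 3 to 23.

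**4. Growth at entry.** Inclusion criterion 7 requires growth of a protocol-defined pathogen, which should make a no-growth baseline rare. Removing the lowest baseline grade shrinks the gain to about 1, 2, 5, 8 and 13 points at underlying r = 0.3 to 0.7. Repeat runs gave 0 to 1 at the low end and 12 to 14 at the high end, stated as about 1 to 12. Removing the two lowest grades leaves about 1, 1, 4, 5 and 7.

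**5. Cross-check on a continuous scale.** Adjustment multiplies the SD by √(1 − r²); a change score multiplies it by √(2(1 − r)). Take an unadjusted comparison with 80% power, so that the difference divided by its standard error is 1.960 + 0.842 = 2.80. At r = 0.5, adjustment gives 2.80 / √0.75 = 3.24, and 3.24 − 1.96 = 1.28, or 90% power. At r = 0.3 a change score gives 2.80 / √1.4 = 2.37, and 2.37 − 1.96 = 0.41, or 66%, against 83.6% adjusted. The ordering matches step 3. The sizes do not carry over to a graded culture.

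**The case against.** The case on the other side has four parts.

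**The size is assumed.** The correlation, the number of grades and the shift are not in the documents, and the entry criterion narrows the baseline. This stands. A reader might take a single figure, such as a loss of 10 to 15 points, from the middle of the table. The documents do not support it: that gain needs a correlation toward the upper end of the assumed range, and with the lowest baseline grade removed only the highest correlation reaches it. What survives is the direction, with gains from negligible to substantial.

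**The rule might be applied to change scores.** Section 9.4.1 does not exclude this, so it would be wrong to say that the plan discards the baseline; it specifies no use of it. Change scores do not rescue the rule, because in step 3 they have less power than the adjusted analysis at every correlation.

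**A culture grade is not a continuous variable.** On a strict reading the normality test in 9.4.1 does not reach it. That is fair, but the endpoint then has no stated method at all, and the remedy is the same. For the same reason, simulations of how often the pre-test misses skewness in continuous data have no bearing here, and none is relied on.

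**LRTI-VAS is covered.** A reader might infer that LRTI-VAS is also left to the t or Mann-Whitney rule. The text does not show this. Section 9.4.4 takes up QOL-B, the Leicester score and LRTI-VAS in turn just after assigning quality of life to the mixed model, so sharing that model is a natural reading. Only the ambiguity stands.

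**Conclusion.** The point holds for bacterial load. It is a listed secondary endpoint without a named model, and the only rule that can reach it is unadjusted, specifies no use of the visit 0 culture, and does not suit an ordered grade. A baseline-adjusted ordinal or rank analysis is better at no cost in data.

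Under the assumptions in step 3, its advantage over Mann-Whitney on follow-up is about 3 to 22 points of power, or about 1 to 12 if entry growth removes the lowest baseline grade. These figures show a range of consequences; they do not estimate this trial's power.

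For LRTI-VAS the finding is unclear wording, with no power loss claimed. The matter is confined to secondary endpoints, for which the trial was not sized. It is worth settling before unblinding because the choice of analysis is otherwise open.

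**What to change.** - **Section 9.4.4, bacterial load.** Name one analysis: a proportional-odds model (or rank analysis of covariance) of the semi-quantitative grade at weeks 26 and 52, containing treatment and baseline category from the visit 0 culture. State the grades to be used.
- **Section 9.4.4, LRTI-VAS.** Say explicitly that it is analysed in the same linear mixed model as quality of life, with its visit 1 value as a covariate.
- **Section 9.4.1.** Exempt efficacy endpoints from the normality pre-test.
- **Any statement of power for these endpoints.** Give it as a range under a stated correlation.

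The cost is a few sentences of analysis text. No visit, sample or measurement is added.
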